## 4.2 Available Therapies for Anemia in Patients with CKD

Erythropoiesis-stimulating agent (ESAs), including epoetin alfa and darbepoetin alfa administered either intravenously or subcutaneously, along with iron therapy are currently the standard of care for treating anemia in patients with CKD. Treatment with exogenous recombinant ESAs can raise Hb, relieve symptoms, and reduce the complications of anemia including avoiding RBC transfusions which carry the risks of infection, iron overload, and impact candidacy for kidney transplantation.

A number of large prospective randomized controlled trials in patients with CKD (GFR categories G3a to G5) have suggested an increased risk of death and cardiovascular (CV) events when targeting higher Hb levels ([Besarab 1998](#), [Druke 2006](#), [Pfeffer 2009a](#), [Pfeffer 2009b](#), [Singh 2006](#)). Additional analyses suggest that the ESAs themselves may be causative of the increased events and not the Hb level, and is supported by studies in CKD patients on dialysis with naturally occurring higher Hb levels and no increase in CV events ([Solomon 2010](#), [Szczech 2008](#), [Goodkin 2011](#)). The risks identified with ESAs from these trials have led to changes in prescribing information and clinical practice guidelines in the USA and Europe.

In the USA, the mortality and CV risks associated with ESAs are outlined in a black-box warning in the prescribing information of ESAs with a recommendation to use the lowest dose possible to avoid transfusions.

The European Union (EU) Summary of Product Characteristics (SmPC) for ESAs suggests caution with the use of ESAs with a recommendation to keep Hb levels between 10-12 g/dL. Furthermore, recent clinical practice guidelines ([Locatelli 2013](#)) recommended that risk factors for stroke (including a past history of stroke) and the presence of active malignancy or a past history of malignancy should be taken into account when making treatment decisions to use ESAs for the treatment of anemia.

Although the CV risk is lower in Japanese subjects compared with Caucasian subjects, guidelines from the Japanese Society of Nephrology ([JSN 2014](#)) stated that ESA treatment targeting Hb levels 12–13 g/dL did not seem to be effective for preventing CKD progression or decreasing the incidence of CV disease compared to the Hb level of 9–11.5 g/dL, but rather had the potential to lead to an increase in the incidence of CV disease.

The risks associated with currently available recombinant ESAs, including an increased risk for death and CV events, highlight the need for novel therapies that may potentially minimize or avoid such risks and slow CKD progression.

[figure not shown]
## 4.3 Hypoxia-Inducible Factor

Hypoxia-inducible factor (HIF) is the primary regulator of the production of RBC and acts by simulating the body's physiologic response to hypoxia ([Haase 2013](#)). HIF proteins are consistently produced and their levels in cells are adjusted by the activity of the HIF-PH enzymes.

During hypoxic conditions, a controlled and coordinated adaptive erythropoietic response occurs whereby, HIF-PH enzyme activity decreases in the kidney and liver, leading to stabilization and increase in intracellular levels of HIF- $\alpha$  proteins. When HIF- $\alpha$  is stabilized, it travels to the nucleus of the cell, where it binds to the protein HIF- $\beta$  ([Figure 1](#)). Dimerized HIF- $\alpha$  and HIF- $\beta$  proteins bind to a promotor on the *EPO* gene to induce an increase in the production of EPO

protein and other proteins. Therefore, stabilization of HIF proteins leads to an increased production of EPO and mobilization of iron to the bone marrow, increasing Hb and RBC production. Inhibitors of HIF-PH enzymes (such as vadadustat) decrease the degradation of HIFs thus mimicking physiological conditions at low oxygen levels.

### Figure 1 Mechanism of Action of Vadadustat

- Normoxia: HIF-PH hydroxylates HIF- $\alpha$  (high level of hydroxylation depicted by 4 arrows), targeting HIF- $\alpha$  for degradation in a VHL (von Hippel-Lindau)-dependent manner, and leading to low levels of HIF- $\alpha$ .
- Hypoxia: HIF-PH activity is decreased (1 dashed arrow). Stabilized HIF- $\alpha$  travels to the cell nucleus, dimerizes with HIF- $\beta$ , and binds to hypoxia response elements (HREs) that control various target genes, including activation of the *EPO* gene leading to increased production of EPO protein.
- By inhibiting HIF-PH activity, vadadustat mimics the physiological effects of hypoxia, leading to increased production of EPO protein and mobilization of iron in the bone marrow, subsequently increasing the level of Hb and RBC production.

Adapted from [Bigham 2014](#)

### 4.4 Description and Mechanism of Action of Vadadustat

Vadadustat works by inhibiting PHD enzymes (Figure 1), leading to stabilization and increased levels of HIF- $\alpha$ , and improved production of Hb and RBCs, while maintaining normal levels of EPO in patients.

Vadadustat has compelling clinical data with several potential safety and efficacy advantages over current injectable recombinant ESA therapy for the treatment of renal anemia:

- Vadadustat significantly increases and maintains Hb levels in CKD patients with anemia:* We have successfully completed two Phase 2 trials in patients with non-dialysis dependent chronic kidney disease (NDD-CKD) which demonstrated that vadadustat significantly increased Hb levels. In the first study (AKB-6548-CI-0005), vadadustat was shown to raise Hb in a dose-dependent manner compared to baseline and across all treatment arms ( $p < 0.0001$ ). In the second Phase 2b study (AKB-6548-CI-0007), vadadustat effectively increased Hb while minimizing Hb excursions  $\geq 13.0$  g/dL. Only

4.3% of patients on vadadustat had a single excursion  $\geq 13.0$  g/dL. In addition, a third Phase 2 trial (AKB-6548-CI-0011) demonstrated the desired outcome of maintaining stable Hb levels in patients with DD-CKD who were converted from existing ESA therapy to vadadustat.

- *Vadadustat restores the normal diurnal variation of EPO:* Instead of binding directly to and saturating the EPO receptor for prolonged periods, as is the case with current injectable ESA therapies, vadadustat acts by simulating the body's natural response to hypoxia by stabilizing HIF- $\alpha$ . Vadadustat allows for an enhancement in the normal diurnal variation in EPO concentration without continuous elevation of EPO levels.
- *Oral, once-daily dosing:* As demonstrated in NDD-CKD patients (Phase 2b Study AKB-6548-CI-0007), vadadustat offers flexible once-daily oral dosing that provides a more gradual and reliable means of Hb response and maintenance. This was also demonstrated in the Phase 2 study AKB-6548-CI-0011 in DD-CKD patients, where vadadustat maintained stable Hb levels in patients converting from ESA therapy. Vadadustat also offers improved convenience for patients as compared to injectable ESAs. This convenience may increase access to anemia therapy and improve patient compliance.
- *Improved mobilization of iron supply to the bone marrow for RBC production:* In clinical trials, vadadustat has demonstrated improved iron mobilization as reflected by a decrease in hepcidin and ferritin levels and an increase in total iron binding capacity. As a result, unlike injectable recombinant ESAs which do not increase iron mobilization, vadadustat offers the added potential benefit of reducing the amount of supplemental iron required by anemic CKD patients. The potential for an intravenous iron sparing effect of vadadustat will be assessed in the global Phase 3 program in DD-CKD patients.
- *Differentiated safety profile:* Vadadustat's novel mechanism of action offers the potential opportunity to reduce the risk for CV and thrombotic events relative to injectable ESAs since CV risks have been associated with supraphysiological increases in EPO levels and excessive Hb fluctuations and/or excursions ([McCullough 2013](#)). The incidence of CV adverse events on vadadustat as compared with ESAs will be assessed in the global Phase 3 program. Furthermore, the risk of pure red cell aplasia (PRCA) observed with recombinant ESAs is not expected with vadadustat.

#### 4.5 Summary of Clinical Experience

*Please see the vadadustat Investigator's Brochure for additional information.*

Overall, vadadustat has demonstrated consistent, dose-proportional pharmacodynamics (PD), producing the desired and anticipated effects of raising EPO concentrations in a dose-dependent manner in both Phase 1 and Phase 2 studies. The changes in EPO have been accompanied by dose-responsive increases in iron mobilization (increased total iron binding capacity [TIBC] and transferrin, and decreased hepcidin and ferritin). Together, these effects stimulated an increase in reticulocytes and Hb. Thus, current data support both an efficacious dose range and a controlled means of dose adjustment for vadadustat that optimizes individualized patient dosing. Additionally, vadadustat has been generally well tolerated.

Vadadustat is eliminated from the body by dual routes of elimination, both renal and fecal, which makes the compound appropriate for use in patients with CKD. Given the dual routes of elimination, it is unlikely that vadadustat will accumulate in patients with CKD. In a clinical study in hemodialysis patients, it was determined that dialysis treatment did not have a notable effect on the PK parameters of vadadustat, indicating that vadadustat can be administered irrespective of the dialysis treatment.

A Phase 2a randomized, placebo-controlled, 6-week, dose range-finding study was performed in subjects with anemia ( $HGB \leq 10.5$  g/dL) secondary to NDD-CKD. The results demonstrated a significant dose-related increase in Hb and TIBC and decreases in hepcidin and ferritin. The plasma concentrations of vadadustat and the glucuronide metabolites exhibited a dose-related increase. Vadadustat was generally well tolerated.

A recently completed Phase 2b, randomized, double-blind, placebo-controlled study to assess the hematologic PD response, safety, and tolerability of oral vadadustat for 20 weeks was performed in 210 subjects with anemia associated with NDD-CKD (AKB-6548-CI-0007). Subjects were assigned to a study group based on their ESA status at screening (naïve, previously treated, or actively treated) and were randomized 2:1 to receive either vadadustat at a starting dose of 450 mg/day or placebo. The dose of vadadustat was adjusted based on Hb levels and changes in Hb. A significantly higher proportion of subjects with a successful Hb response at the end of treatment was observed with vadadustat treatment when compared with placebo ( $p < 0.0001$ ). The dosing algorithm was effective in minimizing excessive Hb levels ( $> 13.0$  g/dL) and a consistent and sustained improvement in iron mobilization was observed with vadadustat treatment. The safety profile of vadadustat in this study was generally consistent with that observed in prior clinical studies.

Based on the Phase 1 and Phase 2 study results, vadadustat is a suitable candidate for continued development as a treatment for anemia in patients with CKD.

#### **4.6 Ethno-Bridging Data from a Study of Healthy Japanese and Caucasian Volunteers**

Study AKB-6548-CI-0020 was a randomized, double-blind, placebo-controlled, dose escalation study conducted at a single clinical site in the United States. The study was conducted to compare the pharmacokinetics (PK) and PD of vadadustat in healthy adult male and female volunteers of Japanese and Caucasian descent.

##### **Brief Overview of Study Design**

The primary study entry criteria included male or female subjects between 20 and 55 years of age, with a body mass index of 18-30  $\text{kg}/\text{m}^2$ , and a body weight of 45-90 kg for Japanese subjects and a body weight of 50-100 kg for Caucasian subjects. For study eligibility, the Caucasian subjects had to be Caucasian of European or Latin American descent. The Japanese subjects had to fulfill the following eligibility criteria: Must have been born in Japan; must have had 2 biological Japanese parents and 4 Japanese grandparents as confirmed by interview; must have been living outside of Japan for up to 10 years at the time of the screening visit; and the subject's lifestyle, including diet, must not have changed significantly since leaving Japan.

[figure not shown]
Eligible subjects were enrolled into one of 3 dose cohorts: 150, 300, or 600 mg daily oral doses of vadadustat (or placebo). Subjects received daily doses of study drug (either vadadustat or placebo) for 10 days. Each of the 3 dose cohorts enrolled 8 Japanese and 8 Caucasian subjects.

Within each dose cohort assignment, subjects were randomized at a 3:1 ratio to receive either vadadustat (n=6) or placebo (n=2).

### Brief Overview of Study Results

Based on the study results, the PK and PD of vadadustat are similar in healthy Caucasian and Japanese subjects with no ethnic factors identified. The mean plasma concentration versus time plot for vadadustat is shown in Figure 2. Although there is a slight increase in the EPO exposure in Japanese subjects at the highest dose (600 mg); this increase is not clinically meaningful. The mean reticulocyte concentrations in subjects of both ethnicities is also similar. EPO levels following vadadustat dosing were within normal physiologic range, at a concentration below EPO receptor saturation, and substantially lower than EPO levels following ESA dosing.

**Figure 2 Mean ( $\pm$  Standard Error) Plasma Concentration versus Time Profiles Following Administration of a Repeated Once Daily Oral Dose of Vadadustat to Healthy Caucasian and Japanese Subjects on Day 10 (Study AKB-6548-CI-0020)**

## 4.7 Potential Benefits and Risks

*Please see the vadadustat Investigator's Brochure for additional discussion and information for the following section.*

Vadadustat offers the potential of flexible oral dosing that is easier to adjust than injectable hormone ESAs. This alternate therapeutic approach may avoid the excursions and fluctuations in Hb levels seen with currently available injectable ESAs and provide for a controlled, steady rise in Hb concentration. This less aggressive approach to modifying the Hb concentration may be of benefit based on suggestion from the US Food and Drug Administration (FDA) that fluctuations in Hb concentrations, rapidly increasing Hb levels, and excursions above the target level are associated with an increased risk of CV events ([Unger 2010](#)).

In addition, HIF activation promotes iron mobilization through upregulation of ferroportin and transferrin and downregulation of hepcidin ([Peyssonnaux 2007](#)). As a result, vadadustat will likely improve iron availability and enhance EPO responsiveness. In the Phase 1b multiple ascending dose study, a prominent effect on iron metabolism was noted with the dosing of vadadustat, including a rapid increase in iron uptake, a dose responsive increase in TIBC, decreases in hepcidin and ferritin, and an increase in transferrin. A similar pattern was observed in the Phase 2a and 2b studies, with dose responsive increases in TIBC and decreases in ferritin and hepcidin.

To date, all of the acute findings observed at doses less than the maximum tolerated dose (MTD) in animals have been shown to be reversible and dose-related. In addition, most of the findings have followed a pattern that would have been predicted based on the known HIF and HIFPH biochemistry, pharmacology, and human genetic variations (eg, Chuvash polycythemia). In the completed clinical studies, vadadustat has been generally well-tolerated.

## 5 STUDY OBJECTIVES AND ENDPOINTS

Note that a pre-treatment value for Hb, hematocrit, RBC count, reticulocyte count, and iron metabolism markers is defined as the average of 2 values obtained prior to treatment, ie, the qualifying screening value and the baseline value.

### 5.1 Primary Objective and Endpoint

The primary objective of this study is to assess the dose-response relationship between oral vadadustat once daily dosing for 6 weeks and the change in Hb in Japanese subjects with anemia secondary to NDD-CKD; in order to define the starting dose for use in Phase 3 clinical studies in Japan.

The primary endpoint that will be used to assess this objective is the mean change in Hb levels from pre-treatment to the end of the primary efficacy period (Week 6).

### 5.2 Secondary Objectives and Endpoints

The secondary objectives of this study are:

- To assess the safety, tolerability, pharmacokinetics (PK), and pharmacodynamics (PD) of oral vadadustat once daily dosing in Japanese subjects with anemia secondary to NDD-CKD during the 6-week, primary efficacy period

- To evaluate the effect of dose adjustments and demonstrate the maintenance effect on Hb during a 10-week maintenance period

The efficacy endpoints that will be used to assess these objectives include the following:

- Proportion of subjects who achieve target Hb 10-12 g/dL at the end of the open-label extension period (Week 16)
- Mean change in Hb between pre-treatment and the end of the open-label extension period (Week 16)
- Mean change in hematocrit, RBC count, and reticulocyte count from pre-treatment to the end of the primary efficacy period (Week 6) and the end of the open-label extension period (Week 16)
- Mean change in iron indices (ie, iron, total iron-binding capacity [TIBC], TSAT, and ferritin) and hepcidin from pre-treatment to the end of the primary efficacy period (Week 6) and the end of the open-label extension period (Week 16)
- Proportion of subjects with confirmed Hb values <10.0 or >12.0 g/dL from pre-treatment to the end of the open-label extension period (Week 16)
- Proportion of subjects requiring rescue with RBC transfusion from baseline to the end of the primary efficacy period (Week 6) and the end of the open-label extension period (Week 16)
- Proportion of subjects requiring rescue with ESAs from baseline to the end of the primary efficacy period (Week 6) and the end of the open-label extension period (Week 16)
- Number of dose adjustments from baseline to the end of the primary efficacy period (Week 6) and the end of the open-label extension period (Week 16)
- Maintenance of iron sufficiency (defined as ferritin  $\geq$ 50 ng/mL and TSAT  $\geq$ 20%) from baseline to the end of the primary efficacy period (Week 6) and the end of the open-label extension period (Week 16)
- Plasma concentration profile of vadadustat and its metabolites using pre-dose sample from Week 4

The safety endpoints that will be used to assess these objectives include the following:

- Safety assessments, including adverse events, vital signs, electrocardiograms (ECGs), and other laboratory assay results (eg, chemistry, components of the complete blood count [CBC] other than the ones noted above, and vascular endothelial growth factor [VEGF])

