### 9.3.9 Week 16 Visit (End-of-treatment visit for the open-label period and early withdrawal visit for withdrawals after Week 10 but before Week 16)

All subjects who received at least 1 dose of open-label vadadustat should complete the Week 16 assessments.

Subjects who withdraw early from the open-label period prior to the Week 16 visit or permanently discontinue study medication prior to the Week 16 visit, should undergo the clinical and laboratory assessments specified below within 1 day of stopping study medication, if possible. Such subjects should also complete the requisite 2-week safety follow-up period (see [Section 9.3.10](#)).

At the Week 16 visit, the following activities/procedures will be performed:

- Vital signs (heart rate and blood pressure should be assessed in a seated position after 5 minutes of rest and prior to blood draws)
- AE review (see [Section 10.3.6](#) for follow-up of unresolved events)
- Concomitant medication review
- Laboratory procedures:
  - Serum pregnancy test for females of childbearing potential (to be analyzed by the central lab)
  - CBC
  - Serum chemistry and eGFR
  - Iron indices
  - Hepcidin

- C-reactive protein
- VEGF
- Subjects should be questioned regarding dosing compliance

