#### 9.3.10 Week 18 Safety Follow-Up Visit (Or 2 Weeks after End-of-Treatment Safety Follow-Up Visit)

For subjects randomized to vadadustat who complete the open-label extension period, the safety visit will be conducted 2 weeks after their end-of-treatment visit (Week 16).

For subjects who discontinue the study early during the primary efficacy period or the blinded dose adjustment and data cleaning period, the safety visit will be conducted 2 weeks after their end-of-treatment visit (Week 10).

At the follow-up visit, the following activities/procedures will be performed:

- Vital signs (heart rate and blood pressure should be assessed in a seated position after 5 minutes of rest and prior to blood draws)
- AE review (see [Section 10.3.6](#) for follow-up of unresolved events)
- Concomitant medication review
- Laboratory procedures:
  - CBC
  - Serum chemistry and eGFR

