## Appendix A: Schedule of Activities

Please refer to [Section 9.2](#) for detailed information regarding the study procedures and evaluations, and please refer to [Section 9.3](#) for detailed information regarding the activities to be performed at each study visit.

	Screening	Primary efficacy period (blinded, fixed-dose treatment) (Day 1-Week 6)					Blinded dose adjustment, data cleaning period (Week 7-10)	Open-label extension period (Week 11-16)		Safety Follow-up (Week 17-18)
Study Week	-4 to 0	Base line	1	2	4	6	10 (EOT, Blinded Period)	14	16 (EOT, Open-Label Period)	18
Study Day	-28 to -4	1	8	15	29	43	71	99	113	127
Visit Window (Days)			±1	±1	±3	±3	±3	±3	±3	±3
Informed consent	X									
Review inclusion/exclusion criteria	X	X								
Individual subject data lock (for subjects who complete Week 6)							X			
Individual subject unblinding (for subjects who complete Week 6)							X			
Demographics, medical history, physical exam, and weight	X									
Vital signs	X	X	X	X	X	X	X	X	X	X
12-lead electrocardiogram		X								
Adverse event review			X	X	X	X	X	X	X	X
Concomitant medication review	X	X	X	X	X	X	X	X	X	X
Serum pregnancy test	X								X	
Urine pregnancy test		X								
Coagulation tests		X								

	Screening	Primary efficacy period (blinded, fixed-dose treatment) (Day 1-Week 6)					Blinded dose adjustment, data cleaning period (Week 7-10)	Open-label extension period (Week 11-16)		Safety Follow-up (Week 17-18)
Study Week	-4 to 0	Base line	1	2	4	6	10 (EOT, Blinded Period)	14	16 (EOT, Open-Label Period)	18
Study Day	-28 to -4	1	8	15	29	43	71	99	113	127
Visit Window (Days)			±1	±1	±3	±3	±3	±3	±3	±3
Folate and vitamin B12	X									
Hb using HemoCue® (Week 10 assessment is not for subjects who discontinue prior to Week 6)			X	X	X	X	X	X		
Complete blood count, including Hb [a]	X	X	X	X	X	X	X	X	X	X
Serum chemistry and eGFR	X	X		X	X	X	X	X	X	X
Iron indices	X	X		X	X	X	X		X	
Hepcidin		X				X	X			X
C-reactive protein		X				X	X			X
VEGF		X				X	X			X
PK pre-dose sample (study drug to be administered after sample collection)					X					
Blinded study drug dispensation, as necessary		X		X	X	X				
Blinded study drug dosing		Blinded study drug dosing								
Vadadustat dispensation, as necessary [b]							X	X		
Vadadustat dosing [b]								Open-label vadadustat dosing		
Study drug compliance check			X	X	X	X	X	X	X	

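### Second protocol version: the schedule table, as read, puts hepcidin, CRP and VEGF at Week 18 but the visit text puts them at Week 16, which exposes the Week 16 hepcidin endpoint at any site working from the table alone

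*Protocol*

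**What the plan says.** The protocol file holds three successive versions. The point concerns the second, whose Appendix A sets Week 16 at Day 113 and Week 18 at Day 127.

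- **Endpoint (Section 5.2).** One secondary endpoint is the mean change in iron indices "and hepcidin from pre-treatment to the end of the primary efficacy period (Week 6) and the end of the open-label extension period (Week 16"). The third version repeats it in the same words.
- **Week 16 visit (Section 9.3.9).** "All subjects who received at least 1 dose of open-label vadadustat should complete the Week 16 assessments". The laboratory list that follows includes hepcidin, CRP and VEGF.
- **Week 18 visit (Section 9.3.10).** The list introduced by "At the follow-up visit, the following activities/procedures will be performed" has two laboratory items: the blood count, and serum chemistry with eGFR.
- **Schedule table (Appendix A).** The hepcidin row reads "Hepcidin X X X X" and the CRP row "C-reactive protein X X X X". The VEGF row has the same pattern. The last mark in each falls under Week 18, and the column headed "16 (EOT, Open-Label Period") is blank. The iron-indices row just above, "Iron indices X X X X X X X", has its last mark at Week 16.
- **Which source governs.** Appendix A tells the reader: "please refer to [Section 9.3](#) for detailed information regarding the activities to be performed at each study visit". Section 9.3 points back to Appendix A for the timing of procedures and asks sites to keep to it, and Section 6.1 cites both. No order of precedence is stated in the text available.

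**The concern.** The table and the visit text of one protocol version give sites opposite instructions for three blood tests, at both Week 16 and Week 18. Vadadustat stops at Week 16. A hepcidin sample drawn at Week 18 therefore reflects the period after treatment and does not measure what the endpoint asks for. A Week 16 sample that was never drawn cannot be recovered. The Week 18 hepcidin value would also come from a different visit than the iron indices named in the same endpoint, which the table does place at Week 16.

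**Working it through.** There is no sample size, power or error rate to reproduce here. The check is a mapping of table cells to visits, followed by a comparison with the text of the same version.

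**1. Alignment.** The table has ten visit columns: Screening, Baseline, and Weeks 1, 2, 4, 6, 10, 14, 16 and 18. The blood-count row carries ten marks in ten cells, which fixes the column positions.

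**2. Mapping and comparison (second version).**

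| Test | Appendix A as read | Section 9.3.9 (Week 16) | Section 9.3.10 (Week 18) |
|---|---|---|---|
| Hepcidin | Baseline, 6, 10, **18** | listed | not listed |
| CRP | Baseline, 6, 10, **18** | listed | not listed |
| VEGF | Baseline, 6, 10, **18** | listed | not listed |
| Iron indices | Screening, Baseline, 2, 4, 6, 10, **16** | listed | not listed |

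Each of the first three rows conflicts with the text twice: a missing mark at Week 16 and an extra one at Week 18. The iron-indices row agrees with the text at both visits.

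**3. First version.** Its Appendix A has CRP and VEGF at Baseline and Weeks 6, 10 and 16. Hepcidin was then part of the iron indices, which were also marked at Week 16. The second version took hepcidin out and gave it a new row directly above CRP and VEGF.

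**4. Could a Week 18 sample stand in for Week 16?** Both visits have a window of ±3 days.

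- Week 16: 113 − 3 to 113 + 3 = Day 110 to 116
- Week 18: 127 − 3 to 127 + 3 = Day 124 to 130
- Nominal gap: 127 − 113 = 14 days
- Smallest gap between the windows: 124 − 116 = 8 days

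The windows do not overlap, so no sample can satisfy both.

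**5. How many subjects.** Only vadadustat subjects enter the open-label extension: 3 groups × 12 = 36 planned. That is the ceiling if every site used the table alone.

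**6. Which analyses.** Section 11.5 plans the hepcidin regression for change to Week 6, and Week 6 is marked in the table. For other visits it plans descriptive summaries. CRP is in no endpoint list. VEGF appears among the safety assessments without a Week 16 time point. The exposed item is therefore one descriptive secondary result: hepcidin change to Week 16.

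**7. After correction.** With the last mark moved to Week 16, each of the three rows reads Baseline, 6, 10, 16. That agrees with Sections 9.3.9 and 9.3.10, with the endpoint, and with the first version's CRP and VEGF rows.

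**The case against.** Three arguments weigh against the point.

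*The table may have been misread.* A mark read one column too far to the right still leaves ten cells, so the cell count proves nothing. The same shift in three adjacent rows fits a reading fault as well as a drafting fault. On the other side, the neighbouring rows align with the visit text, and the new hepcidin row inserted above CRP and VEGF gives a plausible drafting cause. Neither explanation can be ruled out, so this argument stands as a limit on confidence.

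*The second version appears to be superseded.* A reader might infer that the third version carries the same conflict, because it repeats the endpoint. The documents do not show this. The available text of the third version ends in Section 8.1.4, before its visit descriptions and appendix. The schedule was also being edited between versions: the study days for Weeks 10, 14, 16 and 18 went from 81, 109, 123 and 137 to 71, 99, 113 and 127. This argument stands too.

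*The protocol already gives the right instruction.* Appendix A refers to Section 9.3, and the visit text and the endpoint list agree on Week 16. This makes a loss less likely but does not remove the conflict. Section 9.3 sends the site back to the table, and a site that obeys the table is also following the protocol.

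**Conclusion.** The point holds for the second version, in the table as extracted: Appendix A contradicts Sections 9.3.9 and 9.3.10 on hepcidin, CRP and VEGF, and for hepcidin it also contradicts a named Week 16 endpoint. A site using the table alone would lack the on-treatment Week 16 hepcidin value.

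Two larger readings are not supported. A reader might take all 36 vadadustat subjects as lost, but that requires every site to disregard the reference to Section 9.3. A reader might also count three endpoints as damaged, but only hepcidin has a named Week 16 endpoint. The primary endpoint, the dose-response analysis and the Week 6 hepcidin regression do not change.

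Importance is minor to moderate. Confidence is low to medium. It rests on the assumptions that the PDF table was read into the right columns and that the rows were not corrected in the third version.

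**What to change.** First look at the Appendix A table in the original PDF of the second version, and at the same three rows in the third version's Appendix A. If the marks stand at Week 16 in both, nothing needs changing. Where they stand at Week 18, move the hepcidin, CRP and VEGF marks to Week 16 so that the table matches Section 9.3.9 and the endpoint, and notify sites and the central laboratory so that Week 16 kits contain the tubes. If a post-treatment sample was intended, keep the Week 16 draw and add the Week 18 draw to Section 9.3.10 as well.

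The cost is a table correction and a short notice. Moving the marks adds no samples and changes no sample size or analysis; only a deliberate Week 18 draw would add samples.
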